4.3. Removal criteria

Subjects enrolled in this trial who meet one of the following criteria will be removed:

(1) Enrolled subjects who do not satisfy the inclusion criteria/satisfy the exclusion criteria and are wrongly enrolled.

(2) Subjects with serious protocol violations.

4.4. Withdrawal criteria

If any of the following situations occur during this trial, the investigator must discontinue the trial and withdraw the subject. Before withdrawal, the investigator must complete the last evaluation of various markers. The reason and date of the subject's withdrawal will be recorded in detail, and a safety visit shall be performed within 30 days after withdrawal.

- (1) The subject withdraws informed consent and requests to withdraw from the trial;
- (2) Radiological examinations show tumor progression;

*If the subject's clinical disease is stable without significant progression, existing treatment can be continued after a discussion is held with the patient, and informed consent is obtained. Following this, a radiologic evaluation will be performed after 4–6 weeks for confirmation, and treatment can be discontinued if progression is reconfirmed.

- (3) Occurrence of serious adverse events;
- (4) Occurrence of intolerable toxicity;
- (5) Other complications that in the investigator's judgment, make it inappropriate for the subject to continue;
- (6) The subject has poor compliance and does not take the drug on time or at the prescribed dose or does not comply with the study procedures;
- (7) Simultaneous use of other antineoplastic drugs;
- (8) Death of the Subject;
- (9) Loss to follow-up.

5. Investigational Drug and Treatment Design

5.1. Investigational drug

- IBI308

IBI308 (sintilimab) is a sterile injection, and its main active ingredient is recombinant fully human anti-programmed death receptor-1 monoclonal antibody. Its strength is 10 ml:100 mg.

The preparation and infusion of IBI308 (sintilimab) are as follows:

(1) 2 vials of sintilimab injection are removed and added to 100 mL 0.9% (weight/volume) sterile physiological saline solution.

(2) The infusion bag is gently inverted to mix and ensure drug homogeneity in the bag. Avoid vigorous shaking, which will produce bubbles. If a lot of bubbles are produced, leave the bag to stand until the bubbles have disappeared.

(3) The drug is administered through a 0.2–1.2 μm in-line filter (a controlled infusion duration of 30–60 minutes is recommended).

- Anlotinib

Anlotinib hydrochloride tablets (FOCUS V) is a commercially available oral antineoplastic agent. Strengths: 8 mg, 10 mg, and 12 mg. Administration: orally administered with warm water half an hour before breakfast.

5.2 Treatment protocol

- IBI308 (sintilimab) 200 mg/d, d1, intravenous chemotherapy, q3w.

In this study, the administration method for sintilimab is mainly based on safety and exposure (concentration)-response (PD-1 receptor occupancy) relationship data in earlier studies. Under the premise that no significant abnormality in drug clearance is observed in the subject, it is expected that a steady state can be achieved by continuous infusion of BI308 sintilimab 200 mg q3w for 84 consecutive days (4 times). The expected mean trough concentration at steady state is approximately 26 $\mu\text{g/mL}$, and peripheral and target organ PD-1 receptor occupancy can be maintained. The maximum treatment duration of sintilimab is 24 months. During the study, subjects will receive continuous treatment until a protocol-stipulated treatment termination event occurs.

- Anlotinib hydrochloride: 12 mg/tablet, qd, po, d1-d14, q3w.

Until disease progression or an intolerable adverse reaction occurs. If a missed dose occurs, an additional dose should not be taken if the next dose is less than 12 hours. If the investigator determines that continuing oral anlotinib can benefit the patient at the end of the study, oral anlotinib can continue after the patient has signed the informed consent.

6. Dose Modification

6.1. Overall principles

Dose modification must be based on the most severe drug toxicity that occurred in the previous dosing cycle. Three days before each dosing of the investigational drug on Day 1, the blood, liver, and renal function test results of the subject must meet the dosing requirements. All other toxicities must be resolved to CTCAE v4.03 Grade 0–1 or baseline

level (except for alopecia, fatigue, special regulations in the protocol, or other conditions that are deemed not clinically significant by the investigator). If the subject is not dosed as scheduled due to drug toxicity, the next dose can be delayed. If an investigational drug needs to be suspended/permanently discontinued due to investigational drug-related toxicity or other reasons, other investigational drug(s) can be used independently if the corresponding criteria are met. All dose modifications must be recorded in the file, including the reason and management.

AEs related to sintilimab exposure may stem from immunological etiologies. These immune-related AEs (irAEs) may occur within a short period after the first dose or several months after the last dose of sintilimab. They may affect more than one system simultaneously. Based on existing clinical trial data, most irAEs are reversible and can be managed by drug dosing interruption, administration of glucocorticoids, and/or other supportive treatments. For suspected irAEs, an appropriate evaluation must be performed to confirm the etiology or rule out other causes. Other procedures or tests, such as bronchoscopy, endoscopy, or skin biopsy, can be included in this evaluation. Sintilimab will be suspended or permanently discontinued, and glucocorticoids will be administered based on irAE severity. For dose modification and toxicity management guidelines for potential irAE, please refer to the “Management manual for immune-related adverse event” provided by the pharmaceutical company.

6.2. IBI308 (sintilimab) dose modification

Sintilimab dose modification is not permitted during the entire study. Table 3 shows the principles of suspension and permanent discontinuation for sintilimab. If the dose delay occurs during sintilimab treatment (3 weeks per cycle), all future dosing dates will be delayed to ensure that the dosing interval between sintilimab treatment cycles is 21 ± 3 days.

Table 2. Dose modification protocol for IBI308 (sintilimab)-related toxicity

Sintilimab-related adverse events	Severity	Dose modification
Hematological toxicity	Grade 1–3	Drug discontinuation not required
	Grade 4	Drug interruption
Pneumonitis	Grade 2 pneumonitis	Drug interruption
	Recurrent Grade 2 to Grade 4 pneumonitis	Permanent drug discontinuation
Diarrhea/enterocolitis	Grade 2 or 3 diarrhea or enterocolitis	Drug interruption

	Grade 4 diarrhea or enterocolitis	Permanent drug discontinuation
Dermatitis	Grade 3 dermatitis	Drug interruption
	Grade 3–4 dermatitis	Permanent drug discontinuation
Impaired hepatic function	Grade 2 AST, ALT, or TBIL increased in subjects with normal baseline AST, ALT, or TBIL; $\geq 50\%$ increase in AST, ALT, or TBIL (reaching grade 2 requirement) lasting < 7 days in subjects with baseline AST, ALT, or TBIL $> \text{ULN}$.	Drug interruption
	Grade 3 or 4 AST, ALT, or TBIL increased in subjects with normal baseline AST, ALT, or TBIL; $\geq 50\%$ increase in AST, ALT, or TBIL (reaching grade 3 or 4 requirements) lasting ≥ 7 days in subjects with baseline AST, ALT, or TBIL $> \text{ULN}$.	Permanent drug discontinuation
Hypophysitis	Grade 2 hypophysitis	Drug interruption
	Grade 3–4 hypophysitis	Permanent drug discontinuation
Adrenal insufficiency	Grade 2 adrenal insufficiency	Drug interruption
	Grade 3 or 4 adrenal insufficiency	Permanent drug discontinuation
Hyperthyroidism	Grade 3–4 hyperthyroidism	Permanent drug discontinuation
Hyperglycemia	Grade 3 hyperglycemia	Drug interruption
	Grade 4 hyperglycemia	Permanent drug discontinuation
Renal impairment	Grade 2–3 increase of creatinine	Drug interruption
	Grade 4 increase of creatinine	Permanent drug discontinuation
Neurotoxicity	Grade 2 neurotoxicity	Drug interruption
	Grade 3–4 neurotoxicity	Permanent drug discontinuation
Other AEs	First occurrence of other Grade 3 AE	Drug interruption
	Second occurrence of the same Grade 3 AE	Permanent drug discontinuation

Grade 3 AE that cannot be resolved to Grade 0–2/baseline level within 7 days or Grade 0–1/baseline level within 14 days	Permanent drug discontinuation
Grade 4 AE	Permanent drug discontinuation

The maximum suspension period permitted for sintilimab is 12 weeks. If the subject cannot recover to a state in which sintilimab can be used again within 12 weeks, sintilimab will be permanently discontinued, and the follow-up of the subject will begin, except for the following 2 situations:

- Sintilimab suspension for more than 12 weeks due to glucocorticoid use and dose reduction of glucocorticoids for irAE treatment. In this situation, the investigator must discuss and decide whether to continue with sintilimab. Radiologic examination for efficacy evaluation will be performed as scheduled and not affected by drug suspension.
- AE unrelated to sintilimab but related to treatment resulting in sintilimab suspension for more than 12 weeks. In this situation, a discussion with the investigator on whether to continue sintilimab treatment is required. Radiologic examination for efficacy evaluation will be performed as scheduled and not affected by the suspension.

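### Table 2 sends Grade 3 dermatitis both to interruption and to permanent discontinuation of sintilimab, with no qualifier to separate the two rows

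*Protocol*

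**What the plan says.** Protocol 6.2 does not permit changes to the sintilimab dose. Toxicity is handled by suspending the drug or stopping it for good, and Table 2 assigns one of these actions by toxicity and grade.

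The dermatitis entry has two rows:

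- "Grade 3 dermatitis": drug interruption.
- "Grade 3–4 dermatitis": permanent discontinuation.

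The table ends with a block for other adverse events. There, "First occurrence of other Grade 3 AE" leads to interruption. Permanent discontinuation follows "Second occurrence of the same Grade 3 AE", and also "Grade 3 AE that cannot be resolved to Grade 0–2/baseline level within 7 days or Grade 0–1/baseline level within 14 days". Any Grade 4 event in this block is a permanent stop as well.

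The text after the table adds that "The maximum suspension period permitted for sintilimab is 12 weeks", with two exceptions. Section 6.1 says that suspension or discontinuation depends on the severity of the immune-related event, and it refers the reader to a management manual supplied by the company.

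**The concern.** A dose-modification table should give each event one action. Here the same event, Grade 3 dermatitis, has two actions that cannot both be followed: after interruption the drug may be resumed, and after permanent discontinuation it may not.

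The choice matters to the patient. One row allows re-exposure to a PD-1 antibody after a severe skin toxicity. The other permanently removes one of the two study drugs from someone who may be benefiting. Two investigators could act in opposite ways on the same event and both cite Table 2.

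**Working it through.** No arithmetic beyond a comparison of grades applies, and the plan states no figure to reproduce. The check is whether the two rows overlap and whether another rule in the protocol separates them.

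**Step 1. Overlap.** Grades under interruption: {3}. Grades under permanent discontinuation: {3, 4}. Shared: {3}.

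**Step 2. Can one row simply take precedence?** If the stop row always wins, the interruption row covers {3} minus {3, 4}, which is nothing, so that row never applies. If the interruption row wins, the stop row shrinks to {4} and its Grade 3 has no effect. Either way one row is wrong as printed.

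**Step 3. Does another rule decide?**

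| Rule | What it does | What it leaves open |
|---|---|---|
| 4.4, items 3 to 5 | Withdraws subjects with a serious event, intolerable toxicity, or a complication the investigator judges incompatible with continuing | Section 9.5.1 defines seriousness by outcome (such as hospitalization, disability or threat to life), not by grade, so a Grade 3 dermatitis can be non-serious and tolerable |
| 6.1, recovery before dosing | Requires other toxicities to return to Grade 0–1 or baseline, with listed exceptions | Says when a restart may happen, not whether it is allowed |
| 6.1, severity principle | Suspend or stop according to severity | Restates the choice |
| Table 2, first-occurrence row for other events | Interruption | Worded for events other than the named toxicities, so it is no tie-break for dermatitis |
| Table 2, repeat and non-resolution rows | Permanent stop | Even if read as covering dermatitis, they do not reach a first event that resolves in time |
| 6.2, 12-week limit | Caps the length of a suspension | Does not separate the two dermatitis rows |
| 6.5, hand-foot-skin reaction | Reduces the anlotinib dose | Does not concern sintilimab |

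The case left undecided is a first Grade 3 dermatitis that is non-serious, tolerable and resolves in time.

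**Step 4. Does the rest of Table 2 show which row is the slip?** No. "Grade 3 hyperglycemia" leads to interruption, with Grade 4 as the stop, whereas "Grade 3–4 hypophysitis" leads to permanent discontinuation, with Grade 2 as the interruption. Both patterns are in use, so either dermatitis row could be the misprint. Elsewhere, when a grade recurs in an interruption row and a stop row of the same entry, a qualifier separates them: recurrence for Grade 2 pneumonitis, and first against second occurrence for other Grade 3 events. Dermatitis has no such qualifier.

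**Step 5. Could this be a reading fault in the text?** Both rows are complete and each severity is paired with its action. Nothing suggests a broken table.

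**The case against.** The strongest reply is that section 6.1 delegates dose modification for possible immune-related events to the company manual, and that this delegation is part of the protocol. Investigators may therefore have had a clear rule. This stands in part. A reader might infer from Table 2 that investigators were left with no rule at all, but the documents do not show that, because the manual is not among them. What they do show is that the table contradicts itself. Section 6.1 does not say that the manual overrides the table, and an external manual does not make two conflicting protocol rows correct.

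The second reply is that the open case is small. Serious, intolerable or investigator-judged unsuitable cases leave under 4.4, no dose is given before recovery, and this is a single-center trial planned for 23 patients (7 in stage 1 and 16 in stage 2). That is fair and limits the weight of the point. It does not remove it: the rule concerns patient safety, and correcting it takes a change of wording.

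A reader might also infer that the existing rows for other adverse events already protect against a repeat or slow-resolving Grade 3 dermatitis. The table does not clearly support this, since those rows sit under a heading for events not named above. The corrected dermatitis rows should therefore carry these stops themselves.

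**Conclusion.** The inconsistency is real and should be corrected. Table 2 gives Grade 3 dermatitis two incompatible actions, and for a first, non-serious, tolerable event that resolves in time nothing else in the protocol chooses between them.

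Its reach is limited to safety management and exposure to sintilimab. A reader might infer that it weakens the trial's efficacy conclusion. The documents do not support that: the planned sample size, the error rates and the response-rate cut-offs in the two-stage design do not depend on which dermatitis row is followed. No numerical effect can be given, because the protocol states no incidence of Grade 3 dermatitis.

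The conclusion rests on the two rows as printed. It assumes nothing about the manual's content, and which action was intended cannot be settled from the protocol.

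**What to change.** Make the two dermatitis rows mutually exclusive and confirm the split against the company manual.

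The default follows the pattern that Table 2 already uses for other adverse events:

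- First Grade 3 dermatitis: drug interruption.
- Recurrent Grade 3 dermatitis, Grade 3 dermatitis not resolved within the table's existing limits (Grade 0–2 or baseline by 7 days, Grade 0–1 or baseline by 14 days), or any Grade 4 dermatitis: permanent discontinuation.

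A first Grade 3 event then starts as an interruption and becomes a stop only if it recurs or misses a resolution limit, so no event meets both rows at once.

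If the manual requires stopping at the first Grade 3 event, use this instead:

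- Grade 2 dermatitis: drug interruption.
- Grade 3 or 4 dermatitis: permanent discontinuation.

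The two versions answer the restart question differently. The default allows a restart after a first Grade 3 event that resolves; the alternative forbids it and adds an interruption at Grade 2, which the dermatitis rows do not now contain. The manual should therefore be checked before the wording is fixed.

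The cost is that check and the rewording of two table rows. No patients, visits or procedures are added.

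### For patients with abnormal baseline liver tests, Table 2 gives no clear sintilimab action for a Grade 3 or 4 liver rise that has lasted under 7 days; separately, the anlotinib liver table tests least often at Grade 3

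*Protocol*

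**What the plan says.** Section 6.2, Table 2, splits impaired hepatic function by baseline status.

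- **Normal baseline.** Grade 2 leads to interruption. Permanent discontinuation follows for "Grade 3 or 4 AST, ALT, or TBIL increased in subjects with normal baseline AST, ALT, or TBIL". Neither rule depends on duration.
- **Baseline above ULN.** Interruption applies to a rise of at least 50%, described as an "increase in AST, ALT, or TBIL (reaching grade 2 requirement) lasting" less than 7 days. Permanent discontinuation applies to a rise of at least 50%, described as an "increase in AST, ALT, or TBIL (reaching grade 3 or 4 requirements) lasting" 7 days or more. The row has no other line for this group.

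The table ends with Other AEs lines. The first is worded "First occurrence of other Grade 3 AE" and leads to interruption. Later lines permanently discontinue for a repeat of the same Grade 3 event, for a Grade 3 event that resolves too slowly, and for a Grade 4 event. After the table, the text adds: "The maximum suspension period permitted for sintilimab is 12 weeks", with two exceptions.

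Section 6.1 requires that, three days before each Day 1 dose, "the blood, liver, and renal function test results of the subject must meet the dosing requirements". It gives no liver value. Its recovery rule begins "All other toxicities must be resolved to CTCAE v4.03 Grade" 0–1 or baseline, so it covers toxicities other than those laboratory results. For immune-related events it refers to a company manual.

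The hepatic table for anlotinib in Section 6.4 sets liver testing at once a week for Grade 2, once every 2 weeks for Grade 3, and 1–2 times a week for Grade 4.

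**The concern.** The patients concerned can be enrolled. Section 4.1 admits ALT and AST up to 2.5 times ULN (under 5 times with liver metastases) and bilirubin up to 1.5 times ULN.

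Both drugs carry liver rules because liver injury is expected. In this group the sintilimab row tells the site what to do with a recent Grade 2 rise and with a Grade 3 or 4 rise that has persisted for a week. It does not clearly say what to do with a recent Grade 3 or 4 rise. That is the situation the site most often faces when it must decide on a dose, because scheduled chemistry is drawn just before Day 1. The decision then rests on the investigator's reading of the table.

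Stopping anlotinib for the same event does not settle the matter. Section 6.1 lets one drug go on alone when the other is stopped, provided its own criteria are met, and for sintilimab those are the criteria of this row.

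The anlotinib monitoring schedule is a separate fault in another table. The more severe Grade 3 event is checked less often than Grade 2, so worsening or recovery is seen later.

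**Working it through.** No sample size or error rate is involved. The check lists every combination of grade and duration in the hepatic row and reads off the action.

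**Inputs.** Table 2 hepatic row (Section 6.2); the maximum suspension rule (Section 6.2, after the table); timing of the pre-dose panel (Sections 6.1 and 8.2); the anlotinib hepatic table (Section 6.4).

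**Step 1. The grid, for a rise of at least 50% where baseline is above ULN.**

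| Grade | Duration | Normal baseline | Baseline above ULN |
|---|---|---|---|
| 2 | < 7 d | interrupt | interrupt |
| 2 | ≥ 7 d | interrupt | no line, but already held (step 2) |
| 3 | < 7 d | discontinue | **no clear action** |
| 3 | ≥ 7 d | discontinue | discontinue |
| 4 | < 7 d | discontinue | **no clear action** |
| 4 | ≥ 7 d | discontinue | discontinue |

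**Step 2. Grade 2 at 7 days or more.** A rise must last under 7 days before it can last longer, so a Grade 2 rise is interrupted when it is found. Nothing tells the site to resume on day 7. The suspension runs until the patient can be treated again, up to 12 weeks. In effect this cell is filled. The gap is therefore 2 of 6 cells for baseline above ULN, against 0 of 6 for normal baseline.

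**Step 3. Where a newly found rise falls.** Scheduled chemistry is drawn within 3 days before each Day 1. A Grade 3 or 4 rise first seen on that panel has a documented duration on Day 1 of at most 3 days. Since 3 < 7, it lies in the cells without a clear action. A Grade 2 rise found the same way lies in the interrupt cell.

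**Step 4. Can other text fill the two cells?**

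| Possible route | Grade 3, < 7 d | Grade 4, < 7 d |
|---|---|---|
| Read reaching Grade 2 as a minimum that includes Grades 3–4 | interrupt | interrupt |
| Apply the Other AEs lines | interrupt (first occurrence) | discontinue |

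The two routes agree on a first Grade 3 event and conflict at Grade 4. If the Other AEs Grade 4 line did govern liver events, the hepatic row's own 7-day condition at Grade 4 would have no effect. The "Hematological toxicity" row points the same way: it only interrupts at Grade 4, so a named row appears to take precedence over the general line.

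**Step 5. Anlotinib monitoring intervals.** Grade 2: 7 days. Grade 3: 14 days. Grade 4: 7/2 to 7/1 = 3.5 to 7 days. Grade 3 against Grade 2: 14/7 = 2 times as long. Grade 3 against Grade 4: 14/7 to 14/3.5 = 2 to 4 times as long. At Grade 3 anlotinib may resume, at a reduced dose, if the event falls below Grade 2 within 2 weeks, so a 14-day interval gives 14/14 = 1 scheduled test in that window. A test every 14 days also cannot promptly show whether the 7-day limit in Table 2 has been passed.

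**The case against.** The strongest defence is that the row works as a sequence. A Grade 3 or 4 value has also reached the Grade 2 requirement, so sintilimab is interrupted at detection and stopped if Grade 3 or 4 persists for 7 days. If that reading is not accepted, the Other AEs lines apply where the named row is silent; only the first of them contains the word other. Section 6.1 also says that sintilimab is suspended or discontinued according to the severity of an immune-related event, makes dosing conditional on liver results, and refers to a manual that may fill the cells. Section 4.4 withdraws patients for serious adverse events or intolerable toxicity.

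Much of this stands. The sequential reading is reasonable and probably what was meant, and most investigators would hold the drug. It is not what the row clearly says, however. The parallel Grade 3 or 4 wording in the second line suggests that Grade 2 in the first line means Grade 2, and the two fallbacks give different answers at Grade 4. Section 6.1 does not say which action applies at which grade and gives no liver threshold. The content of the manual is not known here.

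A reader might also infer that a Grade 2 rise lasting 7 days or more is left without an action, so that half the grid is empty. The protocol does not support this: the drug is already interrupted by then and stays so until recovery, within the 12-week limit. Nor does it support the inference that dosing through a Grade 3 or 4 rise is directed; no provision says so.

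**Conclusion.** The point holds in a limited form. For patients with baseline AST, ALT or TBIL above ULN, Table 2 gives no clear sintilimab action for a rise of at least 50% reaching Grade 3 or 4 that has lasted under 7 days: 2 of 6 cells, against none for a normal baseline. This rests on taking the row's grades as written. Under the minimum-grade reading both cells would be filled by interruption, which is why the defect is one of clarity and not a proven absence of any rule.

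The monitoring fault needs no interpretation. At Grade 3 the anlotinib table tests liver function at twice the Grade 2 interval and at 2 to 4 times the Grade 4 interval.

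Those affected are the patients among the planned 23 who enter with abnormal liver tests and then have such a rise. The protocol gives no rate, so the number cannot be estimated. The sample size, endpoint and ORR analysis are untouched. The reason to amend is patient safety.

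**What to change.** - In Table 2, for patients with baseline values above ULN: interrupt sintilimab at detection of any rise of at least 50% reaching Grade 2 or higher, whatever its duration. Permanently discontinue if Grade 3 or 4 lasts 7 days or more. The existing 12-week limit then applies to the interruption.
- State whether the Other AEs Grade 4 line applies to hepatic events. Immediate permanent discontinuation at Grade 4 would be a clinical choice that overrides the row's 7-day condition; it is not needed to close the gap.
- In the anlotinib hepatic table, change liver testing at Grade 3 to at least weekly.

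The cost is an edit to two tables and a few extra routine liver panels in patients with Grade 3 events.
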